#### **Double-Blind Phase**

Subjects who continue to meet all entrance criteria will be randomized for study entry at Visit 2 (Day 1). The following procedures will be performed:

#### Visit 2 (Day 1)

1. Review inclusion/exclusion criteria
2. Assess concomitant medications
3. Administer the Medical Outcome Study (MOS) Sleep Scale
4. Administer the Epworth Sleepiness Scale
5. Collect and review sleep and night eating diary
6. Dispense sleep and night eating diary
7. Record adverse events
8. Dispense study medication
9. Schedule return visit in one week

#### Visit 3 (Day 7)

1. Assess concomitant medications
2. Obtain weight
3. Collect and review sleep and night eating diary
4. Dispense sleep and night eating diary
5. Collect study medication and perform drug accountability
6. Record adverse events
7. Dispense study medication
8. Schedule phone contact in one week and return visit in two weeks

#### Telephone contact (Day 14)

1. Assess concomitant medications
2. Discuss sleep and eating diary and remind subject to complete diary daily
3. Discuss medication compliance and remind subject to take medication daily
4. Record adverse events
5. Discuss medication dose and make adjustments if indicated
6. Offer option to come in to clinic for unscheduled visit in the event that subject wishes to discuss adverse events or issues with study protocol and compliance
7. Confirm scheduled return visit in one week

#### Visit 4 (Day 21)

1. Assess concomitant medications
2. Obtain weight
3. Collect and review sleep and night eating diary
4. Dispense sleep and night eating diary
5. Collect study medication and perform drug accountability
6. Record adverse events
7. Dispense study medication
8. Schedule phone contact in one week and return visit in two weeks

#### Telephone Contact (Day 28)

1. Assess concomitant medications
2. Discuss sleep and eating diary and remind subject to complete diary daily
3. Discuss medication compliance and remind subject to take medication daily
4. Record adverse events
5. Discuss medication dose and make adjustments if indicated
6. Offer option to come in to clinic for unscheduled visit in the event that subject wishes to discuss adverse events or issues with study protocol and compliance
7. Confirm scheduled return visit in one week

#### Visit 5 (Day 35)

1. Assess concomitant medications
2. Obtain weight
3. Perform urine pregnancy test (subjects of childbearing potential only)
4. Administer the Medical Outcome Study (MOS) Sleep Scale
5. Administer the Epworth Sleepiness Scale
6. Administer the HAM-D
7. Collect and review sleep and night eating diary
8. Dispense sleep and night eating diary
9. Collect study medication and perform drug accountability
10. Record adverse events
11. Dispense study medication
12. Schedule phone contact in one week and return visit in two weeks

#### Telephone Contact (Day 42)

1. Assess concomitant medications
2. Discuss sleep and eating diary and remind subject to complete diary daily
3. Discuss medication compliance and remind subject to take medication daily
4. Record adverse events
5. Discuss medication dose and make adjustments if indicated

6. Offer option to come in to clinic for unscheduled visit in the event that subject wishes to discuss adverse events or issues with study protocol and compliance
7. Confirm scheduled return visit in one week

#### Visit 6 (Day 49)

1. Assess concomitant medications
2. Obtain weight
3. Collect and review sleep and night eating diary
4. Dispense sleep and night eating diary
5. Collect study medication and perform drug accountability
6. Record adverse events
7. Dispense study medication
8. Schedule phone contact in one week and return visit in two weeks

#### Telephone Contact (Day 56)

1. Assess concomitant medications
2. Discuss sleep and eating diary and remind subject to complete diary daily
3. Discuss medication compliance and remind subject to take medication daily
4. Record adverse events
5. Discuss medication dose and make adjustments if indicated
6. Offer option to come in to clinic for unscheduled visit in the event that subject wishes to discuss adverse events or issues with study protocol and compliance
7. Confirm scheduled return visit in one week

#### Visit 7 (Day 63)

1. Assess concomitant medications
2. Obtain vital signs (sitting blood pressure, pulse, and weight)
3. Perform urine pregnancy test (subjects of childbearing potential only)
4. Administer the Medical Outcome Study (MOS) Sleep Scale
5. Administer the Epworth Sleepiness Scale
6. Collect and review sleep and night eating diary
7. Dispense sleep and night eating diary
8. Collect study medication and perform drug accountability
9. Record adverse events
10. Dispense study medication
11. Schedule return visit in four weeks

#### Telephone Contact (Day 77)

1. Assess concomitant medications
2. Record adverse events
3. Confirm return visit in two weeks

#### Visit 8 (Day 91)

1. Assess concomitant medications
2. Perform physical examination
3. Obtain weight
4. Administer the Medical Outcome Study (MOS) Sleep Scale
5. Administer the Epworth Sleepiness Scale
6. Administer the HAM-D
7. Administer the TFEQ

8. Administer the SDS
9. Obtain blood sample for HbA1C
10. Collect and review sleep and night eating diary
11. Collect study medication and perform drug accountability
12. Record adverse events
13. Dispense medication and instruct the subject on tapering.
14. Schedule Post-Taper Visit 9 (Day 105) in approximately 2 weeks

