### **Inclusion Criteria**

Subjects must satisfy the following criteria before entering the study:

1. Subjects must have a diagnosis of the following for at least 6 months:  
  
Sleep-Related Eating Disorder, defined as (according to ISCD-2 criteria):
  - A. Recurrent episodes of involuntary eating and drinking occur during the main sleep period.
  - B. One or more of the following must be present with the recurrent episodes of involuntary eating and drinking:
    - i. Consumption of peculiar forms or combinations of food or inedible or toxic substances
    - ii. Insomnia related to sleep disruption from repeated episodes of eating, with a complaint of nonrestorative sleep, daytime fatigue, or somnolence
    - iii. Sleep related injury
    - iv. Dangerous behaviors performed while in pursuit of food or while cooking food
    - v. Morning anorexia
    - vi. Adverse health consequences from recurrent binge eating of high-caloric foods
  - C. The disturbance is not better explained by another sleep disorder, medical or neurologic disorder, mental disorder, medication use, or substance use disorder
2. Subjects must experience 3 nights per week of nocturnal eating during the 14-day prospective baseline period prior to Visit 2.
3. Subjects must be between 18 and 75 years of age.
4. Subjects must be able to take oral medication in capsule form, adhere to medication regimens and be willing to return for regular visits.
5. Subjects must have observed the designated washout periods for prohibited medications outlined under the Concomitant Therapy section of this protocol.
6. Female subjects must be:
  - postmenopausal for at least one year, surgically sterile, or
  - practicing an effective method of birth control (e.g., contraceptive injections, intrauterine device, double-barrier method, contraceptive patch, male partner sterilization, abstinence)

and agree to continue abstinence or to use an acceptable method of contraception, as listed above, should sexual activity commence) before entry and throughout the study

- If taking prescription oral contraceptives, must agree to also use a barrier method of birth control throughout the study since topiramate may affect the metabolism of prescription oral contraceptives.
  - Have a negative urine pregnancy test at Visit 2 (Day 1).
7. Subjects must be able to read and comprehend written instructions, and be willing and able to comply with protocol requirements.

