### **Early Withdrawal**

Subject participation may be terminated based upon subject choice, protocol violation (e.g., non-compliance), adverse event, or if a subject is lost to follow-up. The primary reason for withdrawal should be clearly indicated in the subject's study file.

In the event that a subject discontinues prematurely, final visit procedures will be performed at the time of discontinuation, if possible. Subjects who discontinue prematurely should be scheduled promptly for final visit (Visit 8, Day 91) procedures, preferably within 24 hours of the last dose. Subjects should taper study medication as discussed under Study Treatments. All adverse events should be followed to resolution, if possible. All unused study medication must be returned to the investigator.

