#### **All Adverse Events**

All adverse events that occur between the first study-related procedure and within 30 days of the last dose of study medication will be reported. Adverse events will be reported to the PHRC according to their guidelines.

Subjects should report any adverse events voluntarily or in response to general, non-directed questioning (e.g., "How has your health been since the last visit?). For each adverse event reported by the subject, the investigator should obtain all the information required to complete documentation in the subject's research file.

All adverse events, regardless of seriousness, severity, or presumed relationship to study therapy, must be recorded using medical terminology in the subject's study documents. Whenever possible, diagnoses should be given when signs and symptoms are due to a common etiology (e.g., cough,

runny nose, sneezing, sore throat, and head congestion should be reported as “upper respiratory infection”). The investigator must document his/her opinion concerning the relationship of the adverse event to study therapy. All measures required for adverse event management must be recorded in the source document.

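### The last scheduled pregnancy test is on Day 63, so about 42 days of dosing, and every early-withdrawal exit, have no later test

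*Combined protocol and SAP*

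**What the plan says.** **Tests.** The instruction "Perform urine pregnancy test (subjects of childbearing potential only" and its closing bracket appear in the lists for Visit 1 (Day -14), Visit 5 (Day 35) and Visit 7 (Day 63). The Day 77 call, Visit 8 (Day 91) and Visit 9 (Day 105) have no such item. The Time and Events Schedule agrees: its pregnancy test row is marked at Visits 1, 5 and 7 only. Inclusion criterion 6 adds an entry condition, "Have a negative urine pregnancy test at Visit 2 (Day 1", but neither the Visit 2 list nor the schedule row shows that test.

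**Dosing.** Titration and maintenance run 13 weeks, to Day 91. Visit 8 item 13 then reads "Dispense medication and instruct the subject on tapering". The taper lowers the dose by roughly 30% every three days over about 14 days, and Visit 9 is on Day 105.

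**Early withdrawal.** The section says that "final visit procedures will be performed at the time of discontinuation, if possible", identifies these as the Visit 8 procedures, and adds "Subjects should taper study medication as discussed under Study Treatments".

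**Safeguards.** Contraception is required "before entry and throughout the study", with a barrier method added for users of oral contraceptives. Adverse events up to a point "within 30 days of the last dose of study medication will be reported", and on how they are gathered: "Subjects should report any adverse events voluntarily or in response to general, non-directed questioning". The Pregnancies section requires a report within one working day of staff learning of a pregnancy, prompt withdrawal, and follow-up of the outcome and the infant.

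**The concern.** The Toxicology section calls topiramate teratogenic in three animal species, and the Background describes a disorder more common in women with onset in early adulthood. All four maintenance weeks, at the highest dose the titration schedule reaches or at the subject's minimum effective dose, come after the last test, and so does the taper.

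Everything in the Pregnancies section starts from staff knowledge. After Day 63 that knowledge depends on the subject volunteering it, on a general question about her health, or on clinical suspicion. An exposed pregnancy could leave the trial unrecorded and without outcome follow-up, and taper drug could be handed out without a check. What is at stake is safety follow-up. The primary analysis is not touched.

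**Working it through.** The plan states no figure for the untested interval, so there is none to reproduce. The check is day arithmetic on the schedule.

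**Inputs from the protocol**
- Last test: Day 63 (Visit 7 list; Time and Events Schedule).
- End of maintenance: Day 91 (Visit 8; Taper Period).
- End of taper: Day 105, from a taper of about 14 days (Titration Schedule; Visit 9).
- Visit window: 3 days either way (Study Evaluations, General Considerations).
- 40 randomized 1:1, so about 20 on topiramate (Subject Population; Randomization).

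**Dosing days after the last test, completers**
- Now: 105 - 63 = 42 days; 42/105 = 40%. This is 28 days of maintenance (91 - 63) plus 14 of taper (105 - 91).
- Visit window at both ends: (105 - 3) - (63 + 3) = 36 to (105 + 3) - (63 - 3) = 48 days.
- Shorter taper reading: if each step removes 30% of the maintenance dose from Day 91, the dose is 70%, 40% and 10% for three days each and zero from Day 100. Dosing ends near Day 99, and 99 - 63 = 36 days.
- With a Visit 8 test: 105 - 91 = 14 days; 14/105 = 13%. On the shorter taper, 99 - 91 = 8 days. Either way the gain is 28 days.
- Spacing: 63 - 35 = 28 and 91 - 63 = 28, so a Visit 8 test continues the plan's own on-treatment interval.

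**Early withdrawal.** A subject who stops on Day 34, just before Visit 5, has had no on-treatment test. With the full taper she has 34 + 14 = 48 dosing days and no later test. If a site works from the Visit 2 list rather than the inclusion criterion, her last test is on Day -14, about two weeks earlier still.

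**Limit of a urine test.** A very recent conception is missed. Assume a detection lag of 10 to 14 days. Dosing days in which a conception could go undetected:

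| Last test | Calculation | Days |
|---|---|---|
| Visit 7 (now) | 42 + 10 to 42 + 14 | 52-56 |
| Visit 8 | 14 + 10 to 14 + 14 | 24-28 |
| Visit 9 | 0 + 10 to 0 + 14 | 10-14 |

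**Expected count.** Assume 10 to 20 topiramate subjects of childbearing potential and a pregnancy rate of 1% to 10% per year. Neither figure is in the protocol.
- 42-day tail: 10 x 42/365 = 1.15 and 20 x 42/365 = 2.30 woman-years, giving 0.012 to 0.230 pregnancies.
- 28 days gained: 10 x 28/365 = 0.77 and 20 x 28/365 = 1.53 woman-years, giving 0.008 to 0.153 pregnancies.

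These count conceptions in the window. Some would be recognised and reported anyway, so they are upper bounds on the number otherwise missed.

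**The case against.** How often to test is a matter of judgement, and nothing in the documents requires an end-of-treatment test. The plan already has mandatory contraception, a Day 1 entry test, tests on Days 35 and 63, adverse event contacts on Days 77, 91 and 105, a reporting period of 30 days after the last dose, and pregnancy outcome follow-up. Ages run from 18 to 75, and postmenopausal and sterile women are eligible, so 20 exposed subjects of childbearing potential is a ceiling. Conceptions between Days 63 and 91 may come to light by Visit 9 without a test.

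Most of this stands, and it limits the point to a modest safety improvement. It does not close the gap. Contraception lowers the risk but detects nothing. No contact is scheduled after Day 105, so the 30-day period relies on the subject calling in. The Visit 8 list does include a physical examination, but it is not a pregnancy test and the Time and Events Schedule does not mark it at that visit.

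Three stronger readings are tempting, and the documents do not support them:
- *That subjects are unprotected after Day 63.* The safeguards above remain in force; what is missing is a scheduled check.
- *That a Day 91 test would reduce fetal exposure in maintenance.* It comes when maintenance ends. It could affect only the taper and the follow-up.
- *That the plan obliges a pregnant subject to taper.* She must be withdrawn, and withdrawn subjects are told they should taper, with no exception for pregnancy. That wording still leaves room for clinical judgement, so this is a lack of guidance rather than a contradiction.

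**Conclusion.** The point holds as a gap in scheduled detection, confirmed by both the visit lists and the schedule table. About 42 dosing days follow the last test (36 to 48 with visit windows; about 36 on the shorter taper reading), and no early withdrawal has an exit test. The benefit of closing it is real but small: at most about 0.01 to 0.15 pregnancies conceived in the 28 days gained, under the assumed numbers and rates, with fewer that would otherwise be missed. The change is worth making because the test is already in use, the visit already exists, and the plan already commits to following exposed pregnancies. The Day 1 test that the inclusion criterion requires but the Visit 2 list and schedule row omit should be repaired in the same edit.

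**What to change.** 1. In the Visit 8 (Day 91) list, insert the item used at Visit 7 (urine pregnancy test, subjects of childbearing potential) before item 13, and mark it in the Visit 8 column of the Time and Events Schedule. The Early Withdrawal section then carries it to those who attend a final visit. Subjects lost to follow-up stay untested.
2. Amend Visit 8 item 13 so that, for these subjects, taper drug is dispensed only after the result has been reviewed. After a positive result the subject is handled under the Pregnancies section, and the investigator decides whether study drug is tapered or stopped. Placing the condition here covers completers as well as withdrawals.
3. In the same schedule row, mark Visit 2 (Day 1), and add the test to the Visit 2 list, so that both match inclusion criterion 6.
4. Optional: repeat the test at Visit 9. No dosing would then follow the last test, although a very recent conception still could not be excluded.

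Cost: one extra urine test per subject of childbearing potential at an existing visit (two with Visit 9), and a few lines of text. The Day 1 test is already required, so listing it adds nothing to the plan.

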### **Taper Period**

After completion of the titration and maintenance periods (13 weeks), subjects will taper their study medication by decreasing their dose by approximately 30% every three days. Subjects will return for Visit 9 (Day 105) and the following procedures will be performed:

#### **Visit 9 (Day 105)**

1. Assess concomitant medications
2. Obtain weight
3. Record adverse events
4. Collect study medication and perform drug accountability

### **Early Withdrawal**

Subject participation may be terminated based upon subject choice, protocol violation (e.g., non-compliance), adverse event, or if a subject is lost to follow-up. The primary reason for withdrawal should be clearly indicated in the subject's study file.

In the event that a subject discontinues prematurely, final visit procedures will be performed at the time of discontinuation, if possible. Subjects who discontinue prematurely should be scheduled promptly for final visit (Visit 8, Day 91) procedures, preferably within 24 hours of the last dose. Subjects should taper study medication as discussed under Study Treatments. All adverse events should be followed to resolution, if possible. All unused study medication must be returned to the investigator.

### **CONCOMITANT THERAPY**

#### **General**

Subjects may have concurrent illnesses that require prescription or over-the-counter medication during the course of the study. All exclusionary medications taken within 4 weeks (28 days) prior to Visit 1 (Day-14), with the exception of flurazepam and protriptyline which should be recorded within 5 weeks (35 days) and 6 weeks (42 days), respectively, of Visit 1, as well as those continued at the start of the study or started during the study (other than study medication), including the drug name, dose, duration and indication for use, should be recorded in the subjects' study files.

If the patient is taking a prohibited medication, the investigator and patient will discuss the risk and benefits of a trial of tapering and discontinuation of the medication. Any potential medication discontinuation will also be discussed with the prescribing physician.

Modifications to a subject's pre-existing treatment and regimen are not to be made for the explicit purpose of entering this trial, but should be done only where deemed clinically appropriate by the investigator.

The following medications are prohibited during the trial and subjects must observe the designated washout periods prior to Visit 1 (Day -14):

Prohibited Medications Prior to Visit 1 (Day –14) and During the Trial	Washout Period
Anorexic agents for obesity management, including, but not limited to: 
 
• Sibutramine (Meridia®)
 
• Orlistat (Alli™, Xenical®)
 
• Over-the-counter agents such as phentermine, hypericum
 
• Herbal preparations, including but not limited to:
 
• Mah Wang
 
• Ephedra
 
• Herbal-life
 
• Tahitian Noni-Juice
 
	4 weeks
Tricyclic Antidepressants 
 
• imipramine (Tofranil®)
 
• reboxetine (Edronax®)
 
• trimipramine (Surmontil®)
 
	1 week

 
• desipramine (Norpramine®)
 
• amoxapine (Asendin®)
 
• maprotiline
 
• nortriptyline (Pamelor®, Aventyl®)
 
• clomipramine (Anafranil®)
 
• amitriptyline (Elavil®)
 
• doxepin (Sinequan®)
 
	2 weeks

 
• protriptyline (Vivactil®)
 
	6 weeks
Benzodiazepine Receptor Agonists 
 
• zolpidem (Ambien®, Ambien CR®)
 
• eszopiclone (Lunesta®)
 
• zopiclone (Imovane®, Zimovane®)
 
• zaleplon (Sonata®)
 
	2 weeks
Benzodiazepines 
 
• estazolam (Prosom®)
 
• lorazepam (Ativan®)
 
• temazepam (Restoril®)
 
• triazolam (Halcion®)
 
	1 week

 
• alprazolam (Xanax®)
 
	2 weeks

 
• clonazepam (Klonopin®)
 
• clorazepate (Tranxene®)
 
• quazepam (Doral®)
 
	3 weeks

 
• flurazepam (Dalmane®)
 
• chlordiazepoxide (Librium)
 
	5 weeks
Drugs with mixed actions 
 
• mirtazapine (Remeron®)
 
	2 weeks

MAO Inhibitors 
 
• isocarboxazid (Marplan®)
 
• phenelzine (Nardil®)
 
	4 weeks

 
• tranylcypromine (Parnate®)
 
• selegiline hydrochloride (Eldepryl®)
 
	5 weeks
Antiepileptic agents 
 
• topiramate (Topamax®)
 
• phenytoin sodium, phenytoin (Dilantin®)
 
• phenytoin sodium (Phenytek™)
 
• methsuximide (Celontin®)
 
• valproate sodium (Depacon®)
 
• valproic acid (Depakene®)
 
• divalproex sodium, divalproex, valproic acid (Depakote®)
 
• ethosuximide (Zarontin®)
 
• carbamazepine (Tegretol®, Carbatrol®, Eptol®)
 
	3 weeks
Dopamine antagonists 
 
• perphenazine (Trilfon®)
 
• thioridazine (Mellaril®)
 
• trifluoperazine (Stelazine®)
 
• fluphenazine (Prolixin®, Permitil®)
 
	3 weeks

 
• mesoridazine (Serenti®)
 
• chlorpromazine (Thorazine®)
 
• haloperidol (Haldol®)
 
• droperidol (Inapsine®)
 
• thiothixene (Navane®)
 
	3 weeks
Carbonic anhydrase inhibitors 
 
• acetazolamide (Diamox®)
 
• triamterene (Dyazide®, Dyrenium®, Maxzide®)
 
• zonisamide (Zonegran®)
 
	4 weeks
Atypical Antipsychotics 
 
• risperidone (Risperdal®)
 
• olanzapine (Zyprexa®, Zyprexa Zydis®)
 
	4 weeks
Use of an investigational drug or device	4 weeks

\*Chronic use of antacids and the use of calcium supplements greater than the recommended daily dose are prohibited during the trial.

## **ADVERSE EVENTS**

This study follows Partners Health Care guidelines regarding the definitions and reporting policies of adverse events.

Definition: An adverse event is any untoward or unfavorable medical occurrence in a human subject, including any abnormal sign (for example, abnormal physical exam or laboratory finding), symptom, or disease, temporally associated with the subject's participation in the research, whether or not considered related to the subject's participation in the research

(modified from the definition of adverse events in the 1996 International Conference on Harmonization E-6 Guidelines for Good Clinical Practice).

This includes any occurrence that is new in onset or aggravated in severity or frequency from the baseline condition, or abnormal results of diagnostic procedures including laboratory test abnormalities. Any such event is considered an adverse event if it meets any of the following conditions:

- results in discontinuation from the study;
- requires treatment or any other therapeutic intervention;
- requires further diagnostic evaluation (excluding a repetition of the same procedure to confirm the abnormality); or
- is associated with clinical signs or symptoms judged by the investigator to have a significant clinical impact.

Adverse events may or not be related to the study medication or research procedures. Those that are considered related meet the criteria listed below and those that are unrelated are all others that do not. Adverse events may be serious or non-serious. Serious adverse events include those that meet the criteria listed below, and non-serious adverse events include all others. Adverse events may also be unexpected or expected. Unexpected adverse events meet the criteria listed below and expected adverse events are all others that do not.

